Those having access to the data include the study PI and research team personnel. Users are authenticated against MDACC's Active Directory system. External collaborators are given access to the database once approved by the PI, with their access expiring in 6 months but renewable in 6 months increments at the request of the PI. The application is accessed through Secure Socket Layer (SSL). All protected health information (PHI) will be removed from the data when it is exported from REDCap for analysis. All dates for a given patient will be shifted by a randomly generated number between 0 and 364, thus preserving the distance between dates. Dates for each patient will be shifted by a different randomly generated number.

Following publication study data will be archived in REDCap. Since study data may be useful for future research studies performed under separate IRB approved protocols, study data will be archived indefinitely in REDCap. Since REDCap is a secure electronic database with controlled access, and because patient identifiers may be needed to link study data to data from other sources under future IRB approved protocols, patient identifying information will be retained in the archived database.

7. **Sample size:** A sample size of 200 lymph nodes is planned to provide a precise estimate of concordance between 22-G needle and 25-G needle in terms of adequacy and diagnosis. We expect the concordance (as indicated in Table 1) to be greater than 90%. Using the following hypothesis test:  $H_0: p \leq 90\%$  versus  $H_a: p > 90\%$  using a one-sample test.

Table 1. Summary of Concordance for 22 and 25-gauged needles

|                 |              | 22 gauge needle |              |
|-----------------|--------------|-----------------|--------------|
|                 |              | Adequate        | Not adequate |
| 25 gauge needle | Adequate     | a               | b            |
|                 | Not adequate | c               | d            |

$$\text{Concordance} = (a + d)/N$$

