We plan on assessing 200 lymph nodes with 3 interim looks. After the observance of every 50 lymph nodes sequentially, the final analysis plans to use all 200 lymph nodes. Using a one sample binomial test (East v5) to guide the trial, the test parameters considered were as follows: i) 2-Sided, 0.05 Significance Level, and Power of 88%. Assessments will be considered for both futility and superiority. The Lan and DeMets with O'Brien-Flemming type stopping boundaries were used to generate the p-values required to pause the trial for additional patient entry under the circumstances that a futility or superiority boundary is crossed. Note that the stopping boundaries are estimates to guide the trial because the sample size is relative to the number of lymph nodes (not patients), and it is highly expected that one patient will contribute multiple lymph nodes for analysis.

Table 2.

|   | Plan characteristics |
|---|----------------------|
| Assumed Difference                        | 96% versus 90%       |
| 2-sided Test                              |                      |
| Nominal Significance Level                | 0.05                 |
| Power                                     | 88%                  |
| 1 st Interim Analysis (N = 50) |                      |
| P-value to stop for superiority           | < 0.001              |

|  |       |
|--|-------|
| P-value to stop for futility                 | 0.998 |
|  |       |
|  |       |
| 2 nd Interim Analysis (N = 100)   |       |
| P-value to stop for superiority              | 0.003 |
| P-value to stop for futility                 | 0.558 |
|  |       |
|  |       |
| 3 rd Interim Analysis (N = 150)   |       |
| P-value to stop for superiority              | 0.018 |
| P-value to stop for futility                 | 0.159 |
|  |       |
|  |       |
| Final Analysis (N =200) lymph nodes acquired |       |
| P-value to reject H 0             | 0.044 |
|  |       |
|  |       |

We estimate an a priori concordance between the two techniques of 96% (or 192/200), which would yield a 95% CI with 2.25 percentage points as the distance from the observed proportion to the upper limit of the 95% CI, and 3.73 percentage points as the distance from the observed proportion to the lower limit of the 95% CI (noting that the Clopper-Pearson exact 95% CI is not symmetric).

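### Table 2's first-look futility bound (p = 0.998 at N = 50) is almost inert on the normal scale, but at exactly 50 nodes 45/50 meets it, which takes exact power to about 85-86% rather than 88%

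*Combined protocol and SAP*

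**What the plan says.** Section 7 tests a null concordance of at most 90% against a higher value. The assumed value is given as "We estimate an a priori concordance between the two techniques of 96% (or 192/200"). The test parameters are "2-Sided, 0.05 Significance Level, and Power of 88" per cent, from a one-sample binomial test in East v5. On timing the plan says "We plan on assessing 200 lymph nodes with 3 interim looks" and "After the observance of every 50 lymph nodes sequentially, the final analysis plans to use all 200 lymph nodes". On the boundaries it says "The Lan and DeMets with O'Brien-Flemming type stopping boundaries were used to generate the p-values required to pause the trial".

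Table 2 labels the test two-sided. At the first look, N = 50, it prints "P-value to stop for futility | 0.998". The later futility p-values are 0.558 (N = 100) and 0.159 (N = 150). The superiority p-values are below 0.001, then 0.003 and 0.018, with 0.044 at the final analysis.

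Section 7 also says that crossing a boundary pauses entry, and that the boundaries are estimates meant to guide the trial, because the size is counted in nodes and a patient is expected to contribute several. It gives no bound as a count of concordant nodes and no probability of a futility crossing at any look.

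**The concern.** A futility p-value of 0.998 looks like a bound that will practically never be met, and on a continuous scale that is so. The count at 50 nodes is not continuous. Because 50 × 0.90 = 45 is a whole number, one quite ordinary result sits exactly on the null and satisfies the bound. A trial whose true concordance is the plan's own 96% could therefore be paused for futility with a quarter of the planned information, while still having about even odds of success. The plan states no such early-stopping rate, and its 88% power does not allow for it.

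**Working it through.** **Inputs (Section 7 and Table 2).** Null 0.90; assumed 0.96; looks at 50, 100, 150 and 200 nodes; two-sided p-values as listed in Table 2.

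**Reproducing the plan's figure.** I took a normal-scale design with the Table 2 efficacy bounds and a two-sided inner futility band. Futility used O'Brien-Fleming-type error spending, 4 − 4Φ(z_{β/4}/√t), with β = 0.12, null standard error and alternative variance. It returns futility p-values of 0.998, 0.555 and 0.158 (printed 0.998, 0.558, 0.159) and power of 88.1% (printed 88%). So 0.998 is a two-sided value, and 88% is correct on that scale.

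**First look, normal scale.** Two-sided p = 0.998 corresponds to |z| < 0.0025. This is crossed with probability 0.0003 at 96% and 0.002 at 90%.

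**First look, count scale.** z = (x − 45)/√(50 × 0.9 × 0.1) = (x − 45)/√4.5.
- x = 45: z = 0, p = 1.000, so the bound is met.
- x = 44 or 46: |z| = 1/2.121 = 0.471, p = 0.637, so it is not met.

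Under five two-sided p-value definitions (score z, continuity-corrected, exact minimum-likelihood, exact doubled, Wald), 45 is the only count with p of at least 0.998.

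**Probability of meeting it.**
- P(X = 45 | 50, 0.96) = 0.0346.
- P(X ≤ 45 | 50, 0.96) = 0.0490, if the rule is applied directionally.
- P(X = 45 | 50, 0.90) = 0.185.

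**Exact power at 96%.** I added Binomial(50, p) increments over the four looks and removed paths at each crossing, so every pause counts as final. Score-z limits are:
- superiority: none at 50 nodes (even 50/50 gives p = 0.018), then at least 99, 144 and 189;
- futility band: 45, then 89-91 and 130-140. The directional reading stops at 45, 91 and 140 or fewer.

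| Rule | Power with first-look bound | Power without it | Loss |
|---|---|---|---|
| Score z, band | 85.8% | 87.6% | 1.8 points |
| Score z, directional | 85.4% | 87.6% | 2.2 points |
| Exact doubled p, band | 85.1% | 86.7% | 1.6 points |
| Exact doubled p, directional | 84.8% | 86.7% | 1.9 points |

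Across the five definitions the loss is 1.3 to 2.3 points. The one-directional false-positive rate by score z is 1.6% with the bound and 1.7% without.

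**Chance of success from 45/50.** At 96%, (0.8756 − 0.8576)/0.0346 = 0.52 with the later futility looks applied; direct enumeration agrees. Without those looks it is 61%. With them, it is 31% at a true concordance of 95%, 16% at 94%, 7% at 93%, 3% at 92% and 0.4% at 90%.

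**If the look is not at exactly 50.** At 51, 52 or 53 nodes no count has p of at least 0.998, so the literal band stops nothing and costs nothing. The directional reading is met in 1.6% to 1.9% of trials at 96% and costs about 0.4 to 0.5 points.

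**The case against.** **The look may not fall at 50.** Section 3.2 excludes patients in whom only one station is expected to be sampled, and Section 7 expects several nodes per patient, so a look taken when a patient completes may fall at 51-53. This stands: the full effect belongs to a data cut at exactly 50. Table 2 does print N = 50, so that is a fair reading of the plan.

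**The boundaries are a guide.** A reader might infer that the trial must end at 45/50. The documents do not support that: a crossing pauses entry, and judgement remains. But the plan's reason for the caveat is clustering of nodes, not discreteness, and nothing tells the team to disregard 45/50.

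**A one-sided reading.** The hypotheses in Section 7 are directional. Read one-sided, 0.998 means about 38/50 or fewer, which essentially never happens at 96%. That conflicts with Table 2's two-sided label and would give about 94% power, not 88%.

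**45/50 is some evidence of futility.** This stands in part. The even odds hold only if true concordance is 96%; they fall quickly as it nears 90%.

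**The loss is small.** Power stays at about 85% and the false-positive rate hardly moves. That limits the weight of the point.

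**Conclusion.** The point holds, at modest size. With a look at exactly 50 nodes, independent nodes, score-z p-values and every pause treated as final, the printed first-look bound is met in 3.5% of trials at 96% (4.9% directionally), against 0.03% on the normal scale. Exact power is 85.8% or 85.4%; most of the gap to 88% comes from this one entry, since removing it gives 87.6%. With exact doubled p-values removal reaches only 86.7%. Clustering within patients would change the figures, but 45/50 would still equal the null.

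A reader might infer that the 88% was miscalculated. The documents do not support that: it reproduces at 88.1% on the normal scale, and the shortfall arises when the p-values are applied to counts.

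**What to change.** In Table 2, replace the first-look futility entry of 0.998 with no futility stop at N = 50. Leave the later futility bounds, all superiority bounds and the maximum of 200 nodes as they are. In Section 7, give the remaining bounds as counts of concordant nodes, say whether each futility bound is a band or a one-direction cut-off, check them by exact binomial enumeration, and state the resulting exact power. If the first-look stop is kept, restate power as about 85-86%.

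The edit is one table entry and a short addition to the text. The price is less early stopping when concordance is poor. At 90%, expected size rises from about 122 to 136 nodes (band) or from 87 to 119 (directional). At 96% it rises from about 155-156 to 160.

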#### 8. Statistical analysis:

Descriptive statistics will be used to summarize the demographic and clinical characteristics of all patients in the study. The experimental unit is the lymph node, and all analyses will be performed on a per-Lymph node basis. Agreement with respect to the quality (poor, good, or superior) of samples obtained using 22-gauge and 25-gauge needle will be assessed using kappa statistic. Concordance between the 22-gauge and 25-gauge needles with regard to adequacy, diagnosis, and quality of samples will be estimated with exact 95% CIs. Regression modeling with sequence effect and period effect as a covariates will be used to determine the presence of a sequence or period effect. Moreover, we will compute the relative frequency of lymph nodes pertaining to a single patient. Hierarchical modeling will be used, if necessary, to account for within-patient correlation arising from more than one lymph node assessed per patient. Our analyses will be repeated for slides stained using the Romanowsky or Pap technique and for lymph nodes equal to or larger than 1 cm or smaller than 1 cm in short-axis diameter. We will use a two-sided P value of < .05 to define statistical significance. **Consent:** All patients will receive both verbal and written information about the study and will be asked to give informed consent using study-specific consent forms.

**9. Risk to participants:** The use of the new 25-gauge needle which has received FDA approval for use is not anticipated to be increased from the standard EBUS bronchoscopy with the standard 22-gauge needle.

**10. Funding:** The 25-gauge needles will be supplied through an unrestricted research grant from the manufacturer, Boston Scientific. Boston Scientific will have no input into study design, manuscript review or publication.

**11. Cost to participants:** The use of the 22-gauge needles is considered our current standard of care and therefore all expenses related to the bronchoscopy with the exclusion of the 25g-gauge needle will be accrued by the patient and/or insurance as standard patient care related expenses.

[figure not shown]

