## **1. Background**

EBUS-TBNA is a minimally invasive technique that has become standard of care for mediastinal staging of patients with Non Small Cell Lung Cancer. It has been traditionally performed with 22-gauge needles with an excellent diagnostic accuracy and safety profile. Although many have postulated that larger needle channels would increase diagnostic yield, the use of a 21 gauge needle has been shown to reduce sample quality due to excessive blood within the aspirate without effecting diagnostic yield. In fact, a meta-analysis of Endoscopic Ultrasound guided biopsy in solid pancreatic lesions suggested that a smaller 25-gauge needle improves sensitivity for malignancy in comparison to a standard 22-gauge needle. This phenomenon of improving sample adequacy with smaller needle biopsies has also been seen in ultrasonography-guided fine-needle biopsy of the thyroid. Recently, a new 25-gauge EBUS needle (Boston Scientific, Natick, MA, USA) has become available, but no studies so far have compared the utility of this needle with the standard 22-gauge needle for EBUS-TBNA.

**2. Objectives:** To evaluate the utility of the 25-gauge needle relative to the traditionally used 22-gauge needle for sample adequacy and diagnostic yield during EBUS bronchoscopy.

**2.1.** Primary outcome: To determine the degree of concordance in determining sample adequacy and diagnostic yield between the 25-gauge and 22-gauge needle after using 2 passes with each needle size.

**2.2.** Secondary outcomes

- To assess the diagnostic yield obtained with each needle size
- To assess the concordance between each needle size based on diagnostic yield
- To evaluate EBUS-TBNA related complications with each needle size
- To evaluate differences in usability of the different needle sizes, and identify specific lymph node stations that might be more challenging as identified by Likert scale recorded by physicians.

**3. Study Population:** An estimated 120 patients with suspicion of either benign or malignant disease in mediastinal or hilar lymph nodes undergoing EBUS-TBNA for diagnostic purposes or mediastinal staging.

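### The primary concordance test and exact 95% CI treat 200 lymph nodes as independent, and the only adjustment for patient clustering is conditional, with no trigger and no stated role

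*Combined protocol and SAP*

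**What the plan says.** Section 7 (Sample size) states: "A sample size of 200 lymph nodes is planned to provide a precise estimate of concordance". It sets concordance as (a + d)/N, with a null of at most 90% and an assumed value of 96%. Monitoring at 50, 100, 150 and 200 nodes is described as "Using a one sample binomial test (East v5) to guide the trial". The stated power is 88% at two-sided 0.05, and the Clopper-Pearson distances at 192/200 are 3.73 points below and 2.25 above.

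Section 7 also says that "it is highly expected that one patient will contribute multiple lymph nodes for analysis". For that reason it notes that "the stopping boundaries are estimates to guide the trial because the sample size is relative to the number of lymph nodes (not patients". The caveat covers the boundaries only.

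Section 8 (Statistical analysis) states: "The experimental unit is the lymph node, and all analyses will be performed on a per-Lymph node basis". For the interval: "Concordance between the 22-gauge and 25-gauge needles with regard to adequacy, diagnosis, and quality of samples will be estimated with exact 95% CIs". It will tabulate how many nodes come from each patient, and then adds: "Hierarchical modeling will be used, if necessary, to account for within-patient correlation arising from more than one lymph node assessed per patient".

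On cluster size, section 3 gives "An estimated 120 patients with suspicion of either benign or malignant disease in mediastinal or hilar lymph nodes", while section 3.2 excludes patients in whom the clinician expects to sample a single station.

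**The concern.** A binomial test and a Clopper-Pearson interval are valid when nodes are independent. Nodes from one patient share the operator, the needle order (randomised per patient) and the underlying disease, so agreement between needles may be correlated within a patient. If that correlation is positive and ignored, the interval is too narrow and the test against 90% rejects too often.

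The plan sees the issue but does not settle it. It does not say what finding would make the hierarchical model necessary. The table of nodes per patient gives cluster sizes, not correlation, and has no threshold attached. Nor does the plan say whether the model would replace or supplement the test, the exact CI or the interim p-values, or whether it would report overall concordance (a + d)/N. At stake are the nominal level of the primary test and interval, and the meaning of the planning figures.

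**Working it through.** **Inputs from the documents.** 200 nodes; 120 patients; null 90%, alternative 96%; Table 2 superiority p-values <0.001, 0.003, 0.018 and 0.044 at 50, 100, 150 and 200 nodes.

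**Assumptions.** ICC from 0 to 0.5; two or three nodes per patient. The documents imply 200/120 = 1.67 nodes per patient, but the exclusion in section 3.2 points to two or more, which would need at most 200/2 = 100 patients.

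**1. The plan's own figures.** Clopper-Pearson for 192/200 with independent nodes is 92.27% to 98.26%: 96 − 92.27 = 3.73 below and 98.26 − 96 = 2.26 above. This matches the stated 3.73 and 2.25 apart from the last digit, so these are independent-node values.

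**2. Superiority cuts.** With z = (x/n − 0.90)/√(0.09/n) and two-sided p:
- at 50 nodes no result qualifies (50/50 gives p = 0.018);
- at 100 nodes, 99 or more (p = 0.0027; 98 gives 0.0077);
- at 150 nodes, 144 or more (p = 0.014; 143 gives 0.029);
- at 200 nodes, 189 or more (p = 0.034; 188 gives 0.059).

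**3. Error and coverage without adjustment.** For two nodes per patient, P(both concordant) = p² + ICC·p(1 − p), convolved exactly over 25 pairs per look. For three nodes, a beta-binomial with the same ICC. For 1.67 nodes, 80 pairs and 40 single nodes.

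| ICC | 0 | 0.1 | 0.2 | 0.3 | 0.5 |
|---|---|---|---|---|---|
| Upper-side error, two nodes, no futility stopping (nominal 2.5%) | 1.9 | 2.4 | 2.9 | 3.5 | 4.9 |
| CI non-coverage at p = 0.90, 1.67 nodes (nominal 5%) | 3.3 | 4.0 | 4.8 | 5.6 | 7.2 |
| CI non-coverage at p = 0.90, two nodes | 3.3 | 4.2 | 5.2 | 6.2 | 8.3 |
| CI non-coverage at p = 0.90, three nodes | 3.3 | 5.2 | 7.2 | 9.2 | 13.3 |

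Futility stopping is left out because how Table 2's futility p-values apply by direction is a matter of reading. Applying it could only lower the first row.

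**4. Precision.** The design effect is DE = 1 + (m − 1)·ICC. With m = 2 and ICC 0.1, 0.3 and 0.5, DE is 1.1, 1.3 and 1.5, and 200/DE is 182, 154 and 133. Clopper-Pearson at 96% on 200/DE gives lower distances of 3.97, 4.43 and 4.87 points and upper distances of 2.34, 2.49 and 2.63.

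**5. Power.** The unadjusted four-look test without futility has power 90, 89, 88, 87 and 86% over the five ICC values. For an adjusted final-look test with known DE, power = Φ((0.06 − 2.014√(0.09/n_eff))/√(0.0384/n_eff)), with n_eff = 200/(1 + ICC). At ICC 0 this is Φ((0.06 − 0.0427)/0.01386) = Φ(1.247) = 89%. At ICC 0.1, 0.2, 0.3 and 0.5 it is 85, 81, 76 and 67%.

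**6. Would the conclusion change?** Lower 95% limit at the final look, Clopper-Pearson on n/DE:

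| Concordant | DE 1 | DE 1.1 | DE 1.2 | DE 1.3 | DE 1.5 |
|---|---|---|---|---|---|
| 189/200 | 90.37% | 90.12% | 89.87% | 89.63% | 89.16% |
| 190/200 | 91.00% | 90.75% | 90.51% | 90.27% | 89.81% |
| 191/200 | 91.63% | 91.39% | 91.15% | 90.92% | 90.46% |

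The conclusion changes at 189 for DE 1.2 to 1.3, at 189 and 190 for DE 1.5, and nowhere for DE 1.1 or below.

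**The case against.** The plan is open about clustering: section 7 calls the boundaries approximate because of it, and section 8 names both the correlation and a remedy. The exact interval is conservative and absorbs mild clustering. At the documents' own ratio of 1.67 nodes, non-coverage stays at or below 4.8% up to ICC 0.2. Material harm needs an ICC of about 0.3 or more, or larger clusters, and the documents give no ICC. All of this stands, and it limits the weight of the point. It does not remove it, because the section 7 caveat changes no test, interval or planning figure, and the section 8 remedy has no defined use.

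A reader might go further and infer that the plan offers two competing primary intervals, to be chosen once the data are seen. The text does not support that. Section 8 commits to exact CIs for concordance and nowhere offers a model-based one. The hierarchical sentence also follows the sequence and period regression and could be read as belonging to it. What the text supports is narrower: the model's role is undefined, so the exact CI stays unadjusted.

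A reader might also take the 88% as proof that independence was assumed. Step 5 shows that the unadjusted power runs only from 90 to 86% over the whole ICC range, so the figure cannot show this. It simply carries no stated allowance for clustering.

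**Conclusion.** The point holds as a should-fix gap in the specification of the primary analysis. That the method assumes independent nodes, and that the adjustment lacks a trigger and a role, is clear from the text. The size of the harm is conditional on the assumed ICC and cluster size. It is small at two nodes and ICC up to about 0.2. It becomes material from an ICC of about 0.3, where non-coverage is 6.2% at two nodes and 9.2% at three. The documents do not show that the trial's error rate is in fact inflated; that would need an ICC they do not give. At two nodes, the final conclusion is sensitive only at 189 or 190 concordant nodes.

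The expected cluster size also needs settling, since 1.67 nodes per patient sits awkwardly with the single-station exclusion. This is not a strict contradiction: 120 is an estimate, and the exclusion concerns what the clinician expects to sample.

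**What to change.** In section 8, replace the conditional sentence with an unconditional rule: concordance (a + d)/N is tested and estimated with adjustment for patient clustering at each look and at the end. One workable version:

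- **Test:** z = (p̂ − 0.90)/√(0.09·DE/n), compared with the Table 2 p-values.
- **Interval:** Clopper-Pearson with n replaced by n/DE.
- **Design effect:** DE = max(1, patient-clustered variance / binomial variance), and DE = 1 if no node is discordant.
- **Sensitivity analysis:** the unadjusted exact CI.

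In 200,000 simulated trials per setting (two nodes per patient, ICC 0 to 0.5, no futility stopping), this test held upper-side error at 1.7 to 2.1%. Another cluster method suited to small samples would also do. If a hierarchical model is kept, say that it is always used and that it reports overall concordance.

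In section 7, label 88% and 3.73/2.25 as values for independent nodes, and give their range over plausible ICCs and cluster sizes. State the expected nodes per patient, and reconcile it with the 120 patients in section 3 and the exclusion in section 3.2.

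The cost is plan wording and a standard calculation. The downside is a slightly wider CI and a less favourable stated power. No extra patients are requested, but relabelling does not restore power.
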